14.2 POST-OPERATIVE CHEMOTHERAPY

Post-operative chemotherapy is not standard treatment in rectal cancer. Chemotherapy is predominantly applied in randomized clinical trials. It can be part of treatment, as long as patients in each treatment group are treated according to the same protocol. Protocols should be made known to the main coordinating center. Any changes in these protocols during the study period should be reported to and approved by the protocol committee.

14.3 POST-OPERATIVE RADIOTHERAPY

If post-operative radiotherapy is applied, patients in both treatment arms should be treated according to the same protocol. Radiation protocols should be made known to the main coordinating center. Any changes in these protocols should be reported to and approved by the protocol committee.

15 FOLLOW-UP

15.1 FOLLOW-UP VISITS

For the COLOR II trial, clinical examination is performed every year for 7 years. More frequent follow-up visits and other investigations will not be obligatory but on indication or to the preference of the surgeon. At three years after surgery, a CT scan or MRI of the pelvis is performed to exclude local recurrences. Imaging of chest and liver is performed to assess distant metastases. For the sake of interim analysis, recurrences or deaths should be reported by fax to the coordinating center within 2 weeks of detection. Follow-up of patients with recurrent disease should continue at least 3 years after diagnosis of recurrence or until death.

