7 ETHICS

The trial must be approved by the appropriate ethics committee of each participating institution prior to its entry into the study. Eligible patients should be informed in person by the treating surgeon and receive written information about the trial in their own language. Informed consent should be obtained from each patient according to the guidelines of the local ethical committee, prior to randomization into the study. Patients remain free to withdraw at will at any time from the study without giving reasons.

To guarantee optimal treatment for patients in both treatment arms, interim analyses will be performed to compare survival and recurrence in both treatment arms. If differences of survival or recurrence rates are significant, accrual of patients will be stopped.

To assess the feasibility of laparoscopic rectal cancer resection, a phase II trial will precede the accrual of patients in this trial.

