16.2 DEFINITIONS OF LOCOREGIONAL RECURRENCE

- rectal exam positive for rectal cancer
- positive MRI or CT
- positive cytology or histology of adenocarcinoma

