17.6 DATA COLLECTED DURING FOLLOW-UP PERIOD

Once a year the following data will be collected:

- date of visit
- adjuvant therapy
- details on recurrence, including date and method of diagnosis, site of recurrence and treatment consequences
- details on possible complications
- date of death and cause of death

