19 STATISTICAL CONSIDERATIONS

19.1 SAMPLE SIZE AND STATISTICAL ANALYSIS

Locoregional cancer recurrence rate of operated patients with cancer stages <IV after 3 years is currently about 10 %. The primary objective of the study is to show that laparoscopic surgery does not lead to an increased locoregional recurrence rate. Equivalence of both treatments is considered to be shown if the resulting two-sided 95% confidence limits of the difference in 3-yrs locoregional recurrence rates excludes a difference greater than 5%. At a randomization ratio of 2:1, and assuming a recurrence rate of 10% in each group, 850 laparoscopic patients and 425 open patients are required to have a power of 80% for this study.

All analyses will be carried out on an "intention to treat" basis: patients, whose randomized laparoscopic operation was converted to an open resection, will be analyzed in the laparoscopic group.

Eight weeks operative mortality, pathological resection margins and complication rates will be compared using the Chi-square test. Locoregional recurrence rate, disease free survival and overall survival will be compared between the two procedures using log-rank statistic, adjusted for center. Exploratory analysis of the prognostic effects of various baseline data will be done using multivariate Cox-regression. Analysis of the primary endpoint will be performed 1.5 - 2 years after inclusion of all patients.

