19.2 INTERIM ANALYSES

When an obvious difference in recurrence rate or survival between the two treatment groups appears during the inclusion phase of the trial, it is considered unethical to continue accrual of patients.

Formal interim analyses will be carried out after each 20 recurrences and each 20 in-hospital mortalities. For this purpose, recurrences and in-hospital mortalities have to be reported to the coordinating center within 2 weeks after detection.

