- 64. postoperative adjuvant therapy : 0 no
1 yes
- 65. re-admissions : 0 no
(if yes, please fill out event form) 1 yes
- 66. re-interventions : 0 no
(if yes please fill out event form) 1 yes

COLOR II

Dept. of Surgery, QEII Health Sciences Centre
[name]
[name], Halifax, Nova Scotia
Canada [name]
[contact]
[contact]

Date:**Procedure:** LAP / OPEN**Rand nr:****Doctor:**

RECURRENCE FORM

If appropriate, please encircle correct figure, more than one can be encircled per question

107. date of diagnosis of (re)recurrence (dd-mm-yyyy) :
108. number of recurrence (first, second, etc.) :
109. nature of recurrence : 1 locoregional
2 liver metastasis
3 lung metastasis
4 trocar wound recurrence
5 minilaparotomy wound recurrence
6 laparotomy wound recurrence
7 other :
110. date of cancer related death (dd-mm-yyyy) :

**When completed, please fax this form to the coordinating center:
Dalhousie University, Halifax, Canada**

[contact]

COLOR II

Dept. of Surgery, QEII Health Sciences Centre
[name]
[name], Halifax, Nova Scotia
Canada [name]
[contact]
[contact]

Date:**Procedure:** LAP / OPEN**Rand nr:****Doctor:**

RECURRENCE FOLLOW UP FORM**In case of re-recurrence, please fill out a new recurrence form**111. treatment : *(if appropriate, please describe type of procedure)*

0 no

1 curative resection :

2 palliative resection :

3 other :

112. date of cancer related death (dd/mm/yyyy) :

**When completed, please fax this form to the coordinating center:
Dalhousie University, Halifax, Canada**

[contact]

COLOR II

Dept. of Surgery, QEII Health Sciences Centre
[name]
[name], Halifax, Nova Scotia
Canada [name]
[contact]
[contact]

Date:**Procedure:** LAP / OPEN**Rand nr:****Doctor:**

FORM FOR EVENTS**Please don't forget to mention randomization number in upper right corner**

113. Date of event (dd-mm-yyyy) :
114. Sort event :
115. Date of death (dd-mm-yyyy) :
116. Cause of death :
117. Cause of bowel obstruction : 0 no bowel obstruction
1 herniation
2 strangulation
3 non malignant stenosis
4 other
118. Other complication(s) : 0 no
1 incisional hernia
2 complaints of bowel function (other than ileus)
3 other:
119. Date of re-operation (dd-mm-yyyy) :
120. Nature of re-operation :

**When completed, please fax this form to the coordinating center:
Dalhousie University, Halifax, Canada**

[contact]

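### Section 15.1 leaves follow-up beyond the common minimum to the surgeon's preference and does not require it to be the same in both arms

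*Protocol*

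**What the plan says.** Section 15.1 of the Protocol sets a minimum for all patients: a clinical examination each year for 7 years, CT or MRI of the pelvis at 3 years, and further imaging ("Imaging of chest and liver is performed to assess distant metastases"). Beyond that, "More frequent follow-up visits and other investigations will not be obligatory but on indication or to the preference of the surgeon". Section 3.6 also states only a minimum. Neither section, nor 15.2, asks for the additional follow-up to be equal by arm.

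Elsewhere, local freedom comes with an equal-arms rule: pre-operative care (11.2), anesthesia (11.3), analgesia and diet (11.4), pre-operative therapy (14.1), post-operative chemotherapy and radiotherapy (14.2, 14.3) and treatment of recurrence (16.3). Sections 14.1-14.3 and 16.3 also require the local protocols, or changes to them, to be reported.

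The provisions that depend on when a recurrence is found are:

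- Section 16.2 accepts "positive MRI or CT" as locoregional recurrence.
- Section 19.2: "Formal interim analyses will be carried out after each 20 recurrences and each 20 in-hospital mortalities".
- Section 7: "If differences of survival or recurrence rates are significant, accrual of patients will be stopped".
- Section 19.1: locoregional recurrence, disease-free survival and overall survival "will be compared between the two procedures using log-rank statistic, adjusted for center".

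The success criterion in 19.1 is different. It is a 95% confidence interval for the difference in 3-year locoregional recurrence rates, with a 5-point margin.

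On records, 17.6 calls for "details on recurrence, including date and method of diagnosis, site of recurrence and treatment consequences". The printed recurrence form (Appendix VII, items 107-110) has a date of diagnosis but no field for the method. The follow-up form (items 61-66) does not record investigations that were negative.

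**The concern.** Recurrence is dated by its detection, so whoever decides how often to look partly decides when an event occurs. The surgeon knows which operation was done, and the protocol's own rationale is worry about recurrence after a new technique. Closer watching of laparoscopic patients is therefore plausible, though nothing in the document shows that it will happen. The reverse is also possible.

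Stratification by center (section 10) and the center-adjusted log-rank (19.1) deal with hospitals that follow patients differently. They do not deal with a difference between arms inside one hospital.

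Three things would be distorted: the looks at each 20 recurrences, which can stop accrual; the log-rank comparison of locoregional recurrence; and disease-free survival. An analysis plan cannot repair this afterwards, because it cannot equalize visits already made. The difference would be only partly visible in the data, since the forms do not capture negative investigations or the method of diagnosis.

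**Working it through.** **1. The plan's own figure.** Inputs from 19.1: 10% in each arm, margin 5 points, two-sided 95% interval, power 80%, allocation 2:1.

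n(open) = (1.960 + 0.842)² × p(1−p) × (1 + 1/2) / δ² = 7.849 × 0.09 × 1.5 / 0.05² = 423.8, so 424 open + 848 laparoscopic = 1272, against 1275 stated. With 425 and 850, SE = √(0.09/425 + 0.09/850) = 0.01782, and power = Φ(0.05/0.01782 − 1.96) = 80.1%. The sample size reproduces and is not in dispute.

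**2. How far detection moves.** Suppose a share s of recurrences is found by symptoms at onset in both arms and the rest at the next scheduled check. The mean delay for the rest is about 12/2 = 6 months with yearly checks and 6/2 = 3 months with six-monthly checks. The average gap between arms is 3(1−s) months: 3, 1.5 and 0.75 months at s = 0, 0.5 and 0.75.

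**3. Number of looks.** The hazard is λ = −ln(0.9)/3 = 0.0351 per year. With uniform entry over 5 years (assumed), expected onsets during accrual are 1275 × [1 − (1 − e^(−5λ))/(5λ)] = 1275 × 0.0829 ≈ 106. If all are found only at yearly checks, about 85 are detected in that time. That is four to five looks.

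**4. False stops.** Simulation of 10,000 trials per scenario: 1275 patients, 2:1, exponential recurrence with 10% at 3 years in both arms, and an unadjusted log-rank z = (O−E)/√V at each 20 detected locoregional recurrences during accrual. The protocol states no accrual time, boundary, symptom share or schedule difference; all four are assumptions. Chance of stopping with laparoscopic apparently worse:

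| Boundary | s | Yearly in both arms | Half of laparoscopic six-monthly | All laparoscopic six-monthly |
|---|---|---|---|---|
| 1.96 | 0 | 5.2% | 8.9% | 14.7% |
| 1.96 | 0.5 | 5.6% | 7.2% | 9.1% |
| 1.96 | 0.75 | 5.7% | 6.5% | 7.5% |
| 2.5 | 0 | 1.5% | 3.0% | 5.1% |
| 2.5 | 0.5 | 1.7% | 2.3% | 3.1% |
| 2.5 | 0.75 | 1.8% | 2.0% | 2.4% |
| 3.0 | 0 | 0.15% | 0.47% | 0.95% |
| 3.0 | 0.5 | 0.20% | 0.33% | 0.49% |
| 3.0 | 0.75 | 0.29% | 0.32% | 0.34% |

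At 1.96 with accrual of 4 to 6 years, 4.3-6.6% becomes 5.8-14.8%. A second run of 2,000 trials per scenario (5 years, 1.96, all laparoscopic six-monthly) gave 4.6% to 14.3%, 5.3% to 8.3% and 4.9% to 7.5% at the three values of s, in agreement within simulation error. The yearly column exceeds the single-look 2.5% because of repeated looks, which is a separate matter.

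**5. Log-rank at the primary analysis** (1.75 years after last inclusion, first 3,000 trials). Mean z is 0.005 with equal checks. With unequal checks (all / half of laparoscopic patients) it is 0.436 / 0.229 at s = 0, 0.211 / 0.110 at s = 0.5 and 0.105 / 0.056 at s = 0.75, a shift of 0.05 to 0.43. A separate model (600 runs per scenario) let 0%, 30% or 50% of recurrences be found only by imaging. With the laparoscopic arm watched more closely, the apparent hazard ratio is about 1.05, 1.13 and 1.15. With the open arm watched more closely (30% and 50%), it is about 0.90 and 0.87, so the distortion can run either way.

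**6. The 3-year rate difference.** Both schedules have a check at exactly 3 years, so the detected proportions coincide there. In the simulation of step 4 the Kaplan-Meier difference is 0.0003 in every scenario, equal or unequal. This depends on timing. If every 3-year check falls just after the cut, the open arm loses onsets from year 2 on and the laparoscopic arm only those from year 2.5 on. The gap is (1−s) × (0.9^(2/3) − 0.9^(2.5/3)) = (1−s) × (0.9322 − 0.9159) = (1−s) × 1.62 points: 1.6, 0.8 and 0.4 points at s = 0, 0.5 and 0.75, against a 5-point margin.

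**The case against.** The strongest reply is that 15.1 is not like the sections it is compared with. Those fix no content and defer to local practice, so they need an equal-arms rule. Section 15.1 fixes the core schedule centrally for everyone, and only extras are free. Some extras are on clinical indication, which any sensible rule would also leave free. A surgeon's preference is not in itself a preference by arm, and nothing shows that one would arise.

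The top figure of 14.7% also stacks extremes: no symptomatic detection, every laparoscopic patient seen six-monthly, every open patient yearly, and a 1.96 boundary that the protocol does not state. If only a quarter of laparoscopic patients are seen more often, the rise at 1.96 is 5.1% to 6.9%, 5.5% to 6.4% and 5.8% to 6.3% at s = 0, 0.5 and 0.75 (4,000 trials). It is at most 0.6 point at a boundary of 2.5 and 0.1 point at 3.0. The simulated looks count locoregional events only, whereas 16.1 also includes distant disease among recurrences, and the simulated log-rank is not center-adjusted.

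Most of this is fair and limits the weight of the point. The moderate rows are the better guide, and the harm is conditional. But the reply does not supply the missing rule. The extras are what move detection dates, and preference, unlike indication, can be equalized without cost to patients.

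**Conclusion.** The point holds as a conditional weakness. Section 15.1 permits surveillance to differ between arms within a center, and the protocol applies its own equal-arms principle to treatment but not to detection of the primary event.

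Under the stated assumptions, a false stop for laparoscopic harm becomes more likely by roughly 1 to 3.5 points if half of laparoscopic patients are checked twice as often, and by 2 to 9.5 points if all are (5-year accrual, boundary 1.96). At a boundary of 3.0 the rise is below 1 point. The primary confidence interval is essentially protected when 3-year scans are on time and less fully when they run late. Overall survival does not depend on surveillance. The effect on disease-free survival is not quantified, because the protocol gives no rate for it. This merits consideration and is not a flaw that undermines the trial. Confidence is medium, because the size rests on behavior and a boundary that the protocol does not state.

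**What to change.** Add to 15.1 that each center fixes its routine schedule of visits and imaging, applies it identically in both arms, and reports it and any change to the coordinating center. Investigations on clinical indication remain allowed and are marked as such on the follow-up form. Add to the recurrence form the method-of-diagnosis field that 17.6 already calls for. The content of the schedule stays with the center.

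The cost is one sentence and two form fields, with no added visit, scan or patient and no change in sample size. Surgeons lose the freedom to vary routine follow-up from patient to patient. Testing on indication may still differ by arm, but it would then be recorded. The change does nothing about the error from repeated looks, which needs its own remedy.

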6 ENDPOINTS

6.1 PRIMARY ENDPOINT

- locoregional recurrence rate 3 years postoperatively

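### The protocol does not require the 3-year pelvic CT/MRI, the only obligatory pelvic imaging, to be read without knowledge of the allocated operation

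*Protocol*

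**What the plan says.** The primary endpoint (Protocol 6.1) is "locoregional recurrence rate 3 years postoperatively". Section 15.1 requires a yearly clinical examination for seven years and, once, pelvic imaging: "At three years after surgery, a CT scan or MRI of the pelvis is performed to exclude local recurrences". Further visits and tests are left to clinical indication or the surgeon's preference.

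Section 16.2 defines locoregional recurrence by three items: a positive rectal examination, "positive MRI or CT", and positive cytology or histology. It gives no criteria for a positive scan, no equivocal category and no requirement for confirmation.

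The aim in section 19.1 is stated as: "The primary objective of the study is to show that laparoscopic surgery does not lead to an increased locoregional recurrence rate". The decision rule reads "Equivalence of both treatments is considered to be shown if the resulting two-sided 95% confidence limits" of the difference "excludes a difference greater than 5" percentage points.

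Masked reading, central reading and an endpoint committee are not mentioned. The follow-up and recurrence forms in the case record form appendix have a header field that shows whether the procedure was laparoscopic or open.

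**The concern.** Surgeons cannot be masked to the operation, but the person who reads a scan three years later usually can be. Judging whether tumor is present in the pelvis does not require knowing whether the resection was laparoscopic or open. A pelvis altered by surgery, and often by radiotherapy, leaves room for judgement, and that is where knowledge of the arm can influence a call.

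The trial succeeds by showing no increase. Under-calling in the laparoscopic arm would therefore push towards a false conclusion of no increase, and over-calling would push towards failing a technique that is no worse. An analysis plan written later cannot repair this, because masking has to be in place when the scan is read.

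**Working it through.** **Inputs from Protocol 19.1.** Margin 5 percentage points; two-sided 95% limits, hence 2.5% on the harm side; "assuming a recurrence rate of 10% in each group"; "At a randomization ratio of 2:1"; 850 laparoscopic and 425 open patients; power 80%.

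**Step 1: reproduce the plan's sample size.** For one limit against the margin:

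n(open) = [0.10 × 0.90 + (0.10 × 0.90)/2] × (1.960 + 0.842)² / 0.05² = 0.135 × 7.849 / 0.0025 = 423.8, so 424.

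The total is 3 × 424 = 1272, against 1275 stated. Power at 850/425 is 80.1%. Requiring both limits to lie within 5 points would need about 1702, so the plan's figure is in substance a non-inferiority calculation. That form is used below.

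**Step 2: chance of a false pass.** Let the true rates be 15% and 10%, exactly at the margin, and let the laparoscopic rate be read s too low, so that p = 0.15 − s. Then

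SE = √[p(1 − p)/850 + 0.10 × 0.90/425]

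P(pass) = Φ( s/SE − 1.960 ).

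For s = 1 point: SE = 0.0188, s/SE = 0.532, and P = Φ(−1.428) = 7.7%.

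| Net under-call in laparoscopic arm (assumed) | False-pass rate |
|---|---|
| 0 | 2.5% |
| 0.15 point | 3.0% |
| 0.3 point | 3.6% |
| 0.5 point | 4.5% |
| 1 point | 7.7% |
| 2 points | 18.9% |

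Binomial simulation (2,000,000 runs) gives 2.2%, 7.0% and 17.9% at 0, 1 and 2 points, so the normal approximation is adequate.

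**Step 3: bias in the other direction.** With both true rates at 10% and the laparoscopic rate read as 11%, SE = 0.0181 and P(pass) = Φ(0.04/0.0181 − 1.960) = Φ(0.252) = 60%, against 80% without bias.

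**Step 4: how large a misreading each shift needs.** At 15%, the laparoscopic arm has 0.15 × 850 = 127.5 recurrences. One point is 8.5 of them, or 1 in 15. The scan can affect only events that it decides, and the protocol does not say how many those are.

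- If 20% are scan-decided (assumption), that is 25.5 events, and 8.5/25.5 = one third of them would have to be missed in one arm only.
- If 50% are (assumption), that is 63.75 events, and 8.5/63.75 = 13%.
- With 20% scan-decided and a differential miss rate of 5% to 10% (assumption), the shift is 15 × 0.20 × 0.05 to 0.10 = 0.15 to 0.30 point: the 3.0% and 3.6% rows.

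**Step 5: evaluable numbers.** Section 19.1 places the primary analysis 1.5 to 2 years after full inclusion, when the last patients enrolled will not have reached the 3-year scan. If two thirds were evaluable (566/283, an assumption), a 1-point under-call would raise the false-pass rate from 2.5% to 6.4% instead of 7.7%.

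**The case against.** The strongest reply is that the protocol does not establish how much this scan decides.

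- Section 16.2 lists three items without saying that any one suffices. Section 16.1 does accept any one of its criteria for recurrent disease, but its list omits pelvic CT and MRI; locoregional disease appears there through endoscopy, barium enema or tissue. A reader might infer that a positive scan alone makes a primary event. The two sections leave that open.
- A reader might call the scan the only obligatory test for the endpoint. It is not: yearly clinical examination is obligatory too, and a positive rectal examination is a criterion, although 15.1 does not say that the visit includes one. The scan is the only obligatory pelvic imaging.
- A reader might infer that scans are ordered by the treating surgeon, reported locally and read with the arm known. The protocol says none of this. It is silent on who reads and what the reader is told.
- A reader might take the rise from 2.5% to 7.7%, about threefold, as a consequence of the design. It needs a net 1-point bias favouring laparoscopy and a true difference exactly at the margin. The documents support neither figure.

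These objections stand, and they limit the size of the claim. They do not remove the gap: imaging is a listed criterion for the primary endpoint, and nothing protects its reading. Imperfect masking is not a reason for none.

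**Conclusion.** The point holds as a missing safeguard. Masked reading of the 3-year pelvic scan is not required, although imaging is a criterion for the primary endpoint and the outcome forms show the arm. No bias is demonstrated, and its size cannot be estimated from the protocol.

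Under the stated assumptions (true 15% against 10%, 850/425 evaluable, net under-call in the laparoscopic arm), the false-pass rate rises from 2.5% to 3.0–4.5% for shifts of 0.15 to 0.5 point and to 7.7% for 1 point. The lower part of that range may be more realistic, because only imaging-decided recurrences contribute. A 1-point over-call under equality would cost 20 points of power. The change is worth making because it protects the primary claim at little cost.

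**What to change.** Add to section 15.1 that the radiologist who would report the 3-year pelvic scan anyway does so from a standard request. The request gives tumor site, type of resection and anastomosis, and radiotherapy, but not whether surgery was laparoscopic or open. The radiologist records recurrence as yes, no or equivocal before the approach is disclosed. Preferably use the same request text for pelvic scans done on indication before year 3.

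The cost is a sentence in the protocol, a request template and one added form field, since the follow-up form now offers only recurrence no or yes. No extra scan or reader is needed. Masking will be incomplete where scars, clips or earlier records reveal the approach, and the change does not mask rectal examinations or the person completing the recurrence form.
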